3 ABBREVIATIONS

| Abbreviation | Unit | Explanation |
|---------------------|-------------|---------------------------------------|
| ASR | mg/kg/day | Absolute Synthesis Rate |
| Bq | | Becquerel, radiation dose |
| CPAS | g | Cumulative perioperative albumin loss |
| CRF | | Case report form |
| D ₅ -Phe | | Deuterium labeled phenylalanine |
| FSR | %/day | Fractional Synthesis Rate |
| MELD | | Model for End-Stage Liver Disease |
| MPE | | Mol percent excess |
| POD | | Post operative day |

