7.2 SECONDARY QUESTIONS

1. Does perioperative loss on POD7 (4-10) correlate to losses at EOS and POD3?
2. Is cumulative perioperative loss of albumin from plasma still positive at hospital discharge (or POD 21) following liver transplantation?
3. Dichotomize patients in two equally sized groups depending on the amount of cumulative loss of albumin from plasma on EOS, POD3 and POD7 respectively, i.e. to a "leaky" and a "less leaky" group. Which factors predict "leakiness" (demographics, bleeding, fluid balance, ascites, ELISAs etc)?

4. Is cumulative perioperative loss of albumin from plasma positive at EOS, POD3 and POD7 (4-10), respectively, after liver transplantation in children? This is the primary question in the children substudy .
5. Does perioperative loss on POD7 (4-10) correlate to losses at EOS and POD3 in children after liver transplantation?
6. Which factors characterize children with large postoperative drain losses after liver transplantation?
7. Does cumulative perioperative loss of albumin from plasma at EOS, POD3 and POD7 (4-10), respectively, differ between adults in need or not in need of prolonged ICU stay, respectively, after liver transplantation? This is the primary question in the prolonged ICU substudy.
8. Which factors predict “need of prolonged ICU stay” after liver transplantation (demographics, bleeding, fluid balance, ascites etc)?
9. How does synthesis rate of albumin develop during prolonged ICU stay?

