12 SUBJECTS

12.1 INCLUSION CRITERIA

Patients undergoing liver transplantation: adult males and females, and children 0-17 years.

Written informed consent. In children below 12 years consent is only obtained from the parents.

- A. Adults (mass balance, albumin synthesis and ELISAs)
- B. Children (only assessment of losses and gains, no blood sampling except for ELISAs)

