17.2 STATISTICAL ANALYSIS

In a previous study on selected patients undergoing liver transplantation at our department, we found a net leakage of albumin of 37 ± 17 g at end of surgery and of 48 ± 33 g at the third postoperative day. In our hospital, post-operative albumin infusions to keep plasma albumin at 25 g/l are very common, suggestive of ongoing losses in this patient group.

The effect and time course of ischemic liver injury on albumin synthesis has not been investigated, but in the previous pilot study albumin synthesis was higher than normal values on post-operative day 3. All data will be presented as mean with standard deviation (SD) or as median and range of data if not normally distributed.

Furthermore, the mutual correlations between the mass balance albumin parameters and albumin synthesis and P-albumin will be calculated and presented with correlation coefficients. Patients will be dichotomized to “leaky” and “not so leaky”, and possible predictors analyzed by univariate and multivariate logistic regression.

With 103 subjects there is a power of 80% to detect an anticipated effect size of 0.11 with 3 predictors and a 2-sided significance level of 5%. This equals the situation where the 3rd predictor gives an increase in the squared correlation coefficient r^2 from 0.30 to 0.37 or from 0.50 to 0.54. Although this is rather hypothetical it seems likely that such inferences might occur, and we will find them if 2 years production of liver transplants are investigated. If only 2 predictors are used an effect size of 0.095 can be found with 80% power.

Correlations will be reported as Pearson's correlation coefficient r or Spearman's rank correlation r_s depending on the data's nature.

Demographic preoperative data such as age, height, weight, BMI, gender, routine lab, history of weight loss, diagnoses, and current medications will be presented as numbers, averages and standard deviation, or as median range as applicable.

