17.3 DETERMINATION OF THE NUMBER OF SUBJECTS

On page 4 we state that the number of subjects is 240 in the main study. This refers to an overestimation of the total number of liver transplantations during a approximately 2 year period at our hospital and the primary outcome of albumin mass balance.

The primary endpoint of the study (cumulative perioperative albumin shift at POD7) has never been investigated before. On POD3 48 ± 33 g, $p=0.0017$ versus baseline was found in our previous study on selected patients undergoing liver transplantation [Amouzandeh 2017]. This corresponds to a effect size of 1.4. Although data in consecutive patients are likely to be even more scattered a power of 90% is reached with $n=100$ for an effect size of 0.33 with a one sample 2-sided t-test and a significance level of 5%.

We plan to do linear regression with the thus detected “leakiness” as dependent variable and look at possible predictors. We will also dichotomize the patients in “leaky” and “not so leaky” (cut off to be estimated by ROC-curve analysis) and explore possible predictors by logistic regression and multiple logistic regression. The size of the data base becomes important to the quality of the multiple regression procedure, but data quantity will be governed by our patient flow and research resources. Data collection over much more than 2 years is likely to be confounded by changes in routines over time.

The large number of correlations mentioned above must be seen against the background that this is an exploratory pilot study of albumin mass balance and albumin kinetic parameters in liver transplantation. Because this is an unselected patient group for this kind of measurements, there is an intention that the study also should be hypothesis generating.

Sub study A (children, n=20) is included in the above mentioned number.

Sub study B (prolonged ICU stay, n=20) is a cohort included in the main study above.

The expected numbers in substudies A and B are the main reason to extend the whole study to approximately 2 years, and are based on historical records. Although data are likely to be scattered, with n=10-20 there is a reasonable chance to perform statistical inference analysis. The groups will also be compared with the complete data set.

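### The leaky split and predictor models use albumin loss in grams without settling whether children enter or fixing a body-size term, so markers of size could be reported as predictors of leakiness

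*Combined protocol and SAP*

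**What the plan says.** **Scale and population.** Section 3 lists the outcome as "CPAS | g | Cumulative perioperative albumin loss", with no per-kg version. Section 12.1 admits "adult males and females, and children 0-17 years", and Section 9 applies the mass balance to all subjects. Section 17.3 explains the figure of 240, which it calls an overestimate, and adds: "Sub study A (children, n=20) is included in the above mentioned number".

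**Predictor analyses.** Question 3 in Section 7.2 reads: "Dichotomize patients in two equally sized groups depending on the amount of cumulative loss of albumin from plasma". It applies at end of surgery, POD3 and POD7, and it then asks which factors from an open list, starting with demographics, predict membership of the leaky group. Section 17.2 has "possible predictors analyzed by univariate and multivariate logistic regression". Section 17.3 has "We plan to do linear regression with the thus detected" leakiness as the dependent variable. It also has a leaky split defined differently, with "cut off to be estimated by ROC-curve analysis".

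**Body size.** Section 17.2 names "Demographic preoperative data such as age, height, weight, BMI, gender" among the data to be presented. Weight could be tried as one of the demographic predictors, but no section fixes it in a model. Section 11.3 uses anthropometric plasma volume for the absolute synthesis rate, not for CPAS.

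**Sub-studies.** Section 17.3 also compares each sub-study group with the whole data set.

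**The concern.** Identifying predictors of albumin loss is part of the study aim, and Section 17.3 wants the study to generate hypotheses. The outcome is an absolute amount, and the study population runs from infants to large adults. If larger people lose more grams, the leaky half will hold the larger people. Small children would then be labelled less leaky because they are small, and age or height would look like a predictor. In adults alone, height and sex can do the same to a lesser degree. Section 5.3 interprets CPAS as capillary leakage or catabolism, so such a result would be read as physiology when it only reflects size.

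**Working it through.** **1. The plan's own figures.** Regression power uses the noncentral F distribution with noncentrality f²·n. For n=103, f²=0.11 and a joint test of 3 predictors (df 3, 99), power is 79.95%, against a stated 80%. For 2 predictors and f²=0.095 it is 79.4%, also stated as 80%. For the primary one-sample t-test with n=100 and effect size 0.33, noncentrality is 0.33·√100 = 3.3 and power is 90.5%, against a stated 90%. All three reproduce. None depends on whether children enter or on body size.

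**2. Rate at which a pure size marker passes.** The documents give no weights and no relation of CPAS to weight, so the following are assumptions: adults 80±15 kg; children uniform on 5-60 kg; CPAS = 48·(w/80)^b × lognormal error. The error CV is 33/48 = 0.69, from the pilot's POD3 result in Section 17.2. The marker equals (w/80) × lognormal noise with CV 0.5 and is unrelated to loss per kg. CPAS in grams is split at the median, and the leaky label is regressed on the log marker by logistic regression, without and with log weight. There are 1,000 runs per cell. Entries are the share of runs with p<0.05 for the marker.

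| Subjects | Model | b=0 | b=0.5 | b=1 |
|---|---|---|---|---|
| 220 adults + 20 children | marker alone | 4.5% | 51% | 87% |
| | with log weight | 5.1% | 4.5% | 5.9% |
| 93 adults + 10 children | marker alone | 3.6% | 25% | 51% |
| | with log weight | 4.3% | 5.4% | 4.9% |
| 220 adults | marker alone | 4.2% | 9.9% | 24% |
| | with log weight | 4.2% | 4.1% | 4.5% |
| 180 adults | marker alone | 5.1% | 7.6% | 21% |
| | with log weight | 4.9% | 3.8% | 4.1% |

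In the 220+20 case, the share of children in the leaky half falls from 50% (b=0) to 25% and 12%. Correlating the marker with grams directly gives 6.6%, 33% and 65%.

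**3. Named variables.** A second simulation assumed adults of 77±15 kg, age 54±11, 60% male, with heights of 179±7 cm (men) and 166±6.5 cm (women). Adult CPAS was 48±33 g, and age had no effect beyond size. With 180 adults and 20 children and a median split, age reached p<0.05 as follows.

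| Assumed child weights | b=0 | b=0.5 | b=1 |
|---|---|---|---|
| 5-15 kg | 5.8% | 99.8% | 100% |
| 6-50 kg | 6.2% | 69.5% | 96.4% |
| 30-60 kg | 4.8% | 18.6% | 66.3% |

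Moving the cut-off to the 33rd or 67th percentile gives 27-100% for b=0.75-1, so the problem does not depend on which split is used.

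In 180 adults alone, age shows no excess (4.5-6.2%). Height passes in 11.7% (b=0.5) and 36.1% (b=1) of runs, and sex in 8.4% and 20.8%. With weight in the model, height is at 5-6% and sex at 4-5%. A repeat put height at 15% and 33%. Overall, the adult excess is about 8-15% at b=0.5 and 19-33% at b=1; the single 36% cell lies just above that.

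**4. Whether b=0 is plausible across all ages.** Section 5.4 gives 120 g of albumin in 3 L of plasma. Scaled to a 10 kg child from an assumed 70-77 kg adult, the pool is 120·10/77 = 15.6 g to 120·10/70 = 17.1 g. The pilot loss of 48 g is 48/17.1 = 2.8 to 48/15.6 = 3.1 times that pool. Infused albumin can let cumulative loss exceed the pool. So this makes weight-independence doubtful for small children but fixes no value of b.

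**5. Comparison with the complete data set.** The complete mean is (n/N)·group + (1−n/N)·complement. The group-minus-complete difference is therefore (1−n/N) times the group-minus-complement difference. For 20 of 240 the shrinkage is 8.3%; for 20 of 200 it is 10%.

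**The case against.** **Pooling is one reading only.** A reader might infer that the plan puts children into the predictor models. Section 17.3 does not say so. It places sub-study B in the main study but counts sub-study A only in the number. Children also have their own questions 4-6, and Section 22 publishes the sub-studies separately. On the other side, Section 6.2 treats the cohort as one heterogeneous group with subgroups, and the plan writes adults where it means adults (question 7, secondary endpoint C). Neither set of signs settles it. The figure in Section 11.1 is not shown, so the scale used there could not be checked.

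**The estimand.** If bigger patients lose more grams, height does predict grams lost. Calling that misleading assumes that leakiness means loss relative to size. This objection stands, and it is a reason to state which is meant and to report both.

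**Adjustment is possible already.** Weight is collected, demographics are candidate predictors, multivariable models are planned, and the study calls itself exploratory. This limits the severity. It does not ensure that weight is in the model when height, sex or age is reported.

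**Two stronger inferences fail.** The drain losses in Section 5.2 (10-30% of a child's body weight per day) might be taken to show that children leak more per kg. Section 5.3 defines CPAS as loss left over after measured losses such as drains, so they are not evidence on CPAS. It might also be inferred that adjusting for weight is not enough in a pooled model. Rates of up to 77% (logistic) and 96% (linear) for age arose with untransformed weight and an assumed two- to three-fold higher leak per kg in children, for which the documents give no basis. With no such difference, untransformed weight left 5-27%, and log weight left 4-7%.

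**Conclusion.** The gap is real: the analysis set for question 3 is not stated, and no body-size term is fixed for an outcome in grams. The consequence is conditional on loss rising with size. It is strong if children are pooled and modest in adults alone, and it is absent if loss does not depend on size. Every rate above rests on assumed weights and an assumed weight-loss relation, and fewer subjects than 200-240 would lower them.

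A reader might infer that the main result is in doubt. It is not: the one-sample test of CPAS at POD7 and the children's tests against zero do not use the split or the predictors. Given that and the exploratory purpose, the severity is minor to moderate. The overlap with the complete data set is a small additional fault.

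**What to change.** - **Analysis set:** state that the split and the linear and logistic predictor models are run in adults, and describe children under questions 4-6.
- **Body size:** include log body weight, or the anthropometric plasma volume already used in Section 11.3, as a fixed covariate. Report unadjusted grams alongside. Restriction to adults alone does not remove size-tracking by height or sex. Dividing CPAS by weight is not a safe substitute, because it over-corrects if loss is not proportional to weight.
- **If a pooled model is kept:** include log weight and, as a precaution because any child-adult difference per kg is unknown, a child/adult term. With weight and that term, age passed in 4-7% (logistic) and 3-8% (linear) of runs in all settings tried.
- **Cut-off:** use one definition in Sections 7.2 and 17.3. Equal halves needs no reference outcome; an ROC cut-off does, and Section 17.3 names none.
- **Sub-study comparisons:** compare each group with its complement, as question 7 already does for adults.

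The cost is wording only, since weight and height are already collected. Restricting to adults loses 10-20 subjects. The covariates take one or two degrees of freedom from a plan powered for 2-3 predictors. Recorded weight may include ascites, itself a candidate predictor, so the ascites result should be shown with and without weight.

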18 ACCESS TO SOURCE DATA

The primary investigator is responsible that there is a confidentiality agreement between a monitor or any other independent reviewer (*i.e.* auditor) given permission to verify the data in the patient record and the patient record responsible party at Perioperative Medicine and Intensive Care, Karolinska Huddinge. This requires the patient's written consent.

19 ETHICS

19.1 ETHICAL REVIEW BOARD

The investigator is responsible for the application for approval from the Ethics Review Board.

19.2 ETHICAL CONDUCT OF THE STUDY

The study will be conducted according to the study protocol, GCP, regulatory requirements and the Helsinki Declaration.

Our practice is to not suggest a blood sampling protocol to patients that exceeds 100 mL unless the sampling period is prolonged.

20 DATA MANAGEMENT AND ARCHIVE

20.1 CASE REPORT FORMS

Data collected in the study will be recorded in Case Report Forms (CRF) in which the patient is only identified with a code number and initials. The code key kept by the investigator in such a way that unauthorized persons cannot take part of it. Anonymous and coded copies of medical records such as anesthesia records, monitoring sheet for post-operative care, journal text (Take Care) and laboratory lists (Take Care) will also be included in the CRF.

Data collected in the study and registered in the CRF will be transferred to a database that the sponsor is responsible of.

20.2 ARCHIVE

Study documents will be filed at least 10 years after the study report is submitted to the Swedish MPA. The documents should be archived in a legible condition for eventual future audit or inspection by authorities.

21 FINANCIAL SUPPORT AND INSURANCE

The study is funded by research grants. The patients are insured through medical insurance and patient injury insurance.

22 PUBLICATION OF RESULTS

The intention is to publish the results in a scientific journal. The main study and the two planned sub studies will be published separately.

